9.2.2 Serious adverse events (SAEs)

A serious adverse event is any untoward medical occurrence or effect that at any dose:

- results in death;
- is life threatening (at the time of the event);
- requires hospitalisation or prolongation of existing inpatients' hospitalisation;
- results in persistent or significant disability or incapacity;
- is a congenital anomaly or birth defect;
- Any other important medical event that may not result in death, be life threatening, or require hospitalization, may be considered a serious adverse experience when, based upon appropriate medical judgement, the event may jeopardize the subject or may require an intervention to prevent one of the outcomes listed above.

Medical and scientific judgment should be exercised in deciding whether an AE is serious in other instances, such as an important medical event that may not be immediately life-threatening or resulting in death, or a hospitalisation that may jeopardize the subject or require intervention to prevent one of the above outcomes.

All serious adverse events will be reported by the investigator to the **Accelovance Pharmacovigilance (PV)** within 24 hours of first knowledge of the Investigator via the **Fax:** [REDACTED]

All SAEs will be reported by submitting a completed SAE Report Form. Whenever possible, diagnoses should be given when signs and symptoms are due to a common etiology. It is critical that the information provided on the Sponsor's SAE Report Form matches the information recorded in AE eCRF

for the same event. In addition, the same information is to be recorded in the source documents.

The Investigator must also notify the Independent Ethics Committee (IEC) or Institutional Review Board (IRB) in writing as soon as is practical, but at least within 15 Days after the Investigator has first knowledge of the serious adverse events.

Accelovance PV will notify Sponsor of all SAE's within 24 hrs of its initial receipt.

The Council for International Organizations of Medical Sciences (CIOMS) Form prepared by Accelovance PV will be shared with Sponsor for review and approval.

Pregnancy test will be performed at screening and at visits specified in the protocol. Subjects with a positive test at screening or during the study period will be excluded from the study. Women of child-bearing potential will be instructed to practice an acceptable method of birth control for the duration of the study. However, if subject becomes pregnant during the study, pregnancy will be recorded as a significant medical event and reported per SAE reporting procedure. The outcome of a pregnancy should be followed up carefully and any abnormal outcome of the pregnancy should be reported. Subjects who become pregnant during the study will be asked to discontinue the study drug if this can be done safely.

SAEs that result in death or are life threatening should be reported expeditedly. The expedited reporting will occur not later than 7 Days after the responsible investigator has first knowledge of the adverse event. This is for a preliminary report with another 8 Days for completion of the report.

9.2.3 Suspected unexpected serious adverse reactions (SUSARs)

Adverse reactions are all untoward and unintended responses to an IMP related to any dose administered.

Unexpected adverse reactions are SUSARs if the following three conditions are met:

1. the event must be serious (see chapter 9.2.2);
2. there must be a certain degree of probability that the event is a harmful and an undesirable reaction to the medicinal product under investigation, regardless of the administered dose;
3. the adverse reaction must be unexpected, that is to say, the nature and severity of the adverse reaction are not in agreement with the product information as recorded in:

- Summary of Product Characteristics (SPC) for an authorised medicinal product;
- Investigator's Brochure for an unauthorised medicinal product.

The time frame for submitting suspected, unexpected serious adverse drug reaction or other information which qualifies for reporting to European Medicines Agency (EMA) and all participating investigators is no later than 15 calendar days after initial receipt of the information by Accelovance PV.

Suspected and Unexpected fatal or life-threatening adverse reactions represent especially important safety information and, therefore, must be reported more rapidly to EMA. The requirement for reporting any Suspected and Unexpected fatal or life-threatening adverse reaction to EMA is no later than 7 calendar days after initial receipt of the information by Accelovance PV. If the safety report submitted within 7 calendar days is complete, an additional submission within 15 days from day zero is not required.

Accelovance PV will report any suspected unexpected serious adverse reactions (SUSARs) on behalf of the Sponsor to the IEC/CA according to local requirements.

The IRB/IEC should receive the following SUSARs expeditedly:

- SUSARs that have arisen in the clinical trial that was assessed by the IEC
- SUSARs that have arisen in other clinical trials of the same Sponsor and with the same medicinal product, and that could have consequences for the safety of the subjects involved in the clinical trial that was assessed by the IEC

The remaining SUSARs are recorded in an overview list (line-listing) that will be submitted once every half year to the IEC. This line-listing provides an overview of all SUSARs from the study medicine, accompanied by a brief report highlighting the main points of concern.

Premature unblinding of study drug may occur to reveal whether a subject has been treated with Nanocort or Depo-Medrol®, Unblinding should occur only in an emergency and if the information is considered by the Investigator (or other treating physician) as medically necessary. If unblinding occurs prior to notification of the Medical Monitor the circumstances leading to the unblinding must be clearly documented and promptly reported by telephone or in writing to the Medical Monitor.

Development Safety Update Report

In addition to the expedited reporting of SUSARs, Accelovance Pharmacovigilance will submit, once a year throughout the clinical trial, a safety report to the accredited ethical committee competent authority, and competent authorities of the concerned Member States. This safety report consists of:

- a list of all suspected (unexpected or expected) serious adverse reactions, along with an aggregated summary table of all reported serious adverse reactions, ordered by organ system, per study;
- a report concerning the safety of the subjects, consisting of a complete safety analysis and an evaluation of the balance between the efficacy and the harmfulness of the medicine under investigation.

9.3 Follow-up of adverse events

All AEs will be followed until they have abated, or until a stable situation has been reached. Depending on the event, follow up may require additional tests or medical procedures as indicated, and/or referral to the general physician or a medical specialist.

SAEs need to be reported till end of study.

9.4 Data Safety Monitoring Board (DSMB) / Safety Committee

DSMB is not planned for this study. Nanocort contains prednisolone. Prednisolone is in clinical use for years. The reference product, Depo-Medrol, which contains methylprednisolone, is also clinically used in current practice for the treatment of a variety of diseases. Considering the known safety profile of prednisolone or methylprednisolone in clinical use, DSMB is not planned.

10. STATISTICAL ANALYSIS

10.1 General

Descriptive statistics, including the number and percentage for categorical variables, and the number, mean, standard deviation (SD), median, minimum and maximum for continuous variables will be provided. Listings of individual subjects' data will be produced. Where appropriate time trends will be shown by graphically displays.

For continuous data, one-way Analysis of variance (ANOVA) (in case of normally distributed variables) or the non-parametric Kruskal-Wallis test will be used; for categorical data and binary data the Chi-square test or Fisher's exact test will be used.

A detailed Statistical Analysis Plan (SAP) will be written and finalized in advance of database lock. All the details necessary to complete the statistical analyses will be provided in the SAP. This SAP should be approved by the Sponsor and MM (or designee) prior to un-blinding.

The statistical package SAS® v9.3 or higher will be used to produce all summary tables and data listings and to perform the hypotheses testing.

10.2 Primary study parameter

EULAR responders (good and moderate combined) at Day 8

EULAR responders (good and moderate combined) at Day 8 will be summarized by treatment group and pair-wise compared between both Nanocort arms and the Depo-Medrol arm using the Cochrane-Mantel-Haenszel test stratified by study site.

As sensitivity analysis a logistic regression model will be fitted on the EULAR responders with the stratification factor study site and additional baseline variables as covariates.. Proportional odds ratios will be presented. The SAP will specify the planned additional covariates .

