4. STUDY POPULATION

4.1 Population

The study will be conducted at approximately 25 sites in the Netherlands, Belgium and the Czech Republic. Sites will be selected based on previous study experience in RA and accessibility to study required populations. It is expected that each research centre will be able to identify sufficient subjects that meet all the inclusion and exclusion criteria.

The study population will consist of male and female subjects (≥ 18 years old) with active RA who are experiencing a flare / exacerbation defined as recently switched from a period with - well documented- remission or low disease activity to an active disease (DAS28 ≥ 3.2). This documentation is either based on available detailed DAS28 values (increase in DAS28 > 1.2 or > 0.6 if DAS28 ≥ 3.2 compared to last DAS28 measurement (maximum 06 months before), or on a clear description of the previous low disease state by the treating physician (maximum 06 months before). The increase in disease activity has to be RA related.

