4.4 Sample size calculation

A total of 330 subjects will be enrolled and randomized into 3 groups of 110 subjects.

The EULAR response will be considered as primary parameter.

There is a special interest in the percentage of subjects with an EULAR response category of good or moderate (good and moderate combined) and the percentage of subjects with an EULAR response category of only good. These subjects will be called **EULAR responders** and **EULAR good-responders**, respectively.

Primary endpoint:

- the percentage of EULAR responders (good and moderate combined) at Day 8

Key secondary endpoints:

[figure not shown]
- The percentage of EULAR good-responders at Day 8
- The percentage of EULAR responders at Day 15
- The percentage of EULAR good-responders at Day 15

The sample size calculation for this study is based on group comparisons of EULAR responder rates (Nanocort 150 mg compared to Depo-Medrol® and Nanocort 75 mg compared to Depo-Medrol®) at Day 8. The study is called positive if one of the primary null hypotheses will be rejected.

The following primary null hypotheses will be considered:

$H_{0,1}$: EULAR responder rate at Day 8 for Nanocort 150 mg = EULAR responder rate at Day 8 for Depo-Medrol®

$H_{0,2}$: EULAR responder rate at Day 8 for Nanocort 75 mg = EULAR responder rate at Day 8 for Depo-Medrol®

Taking a drop-out rate of approximately 10% into consideration, a sample size of 110 subjects per treatment arm will be sufficiently large to show superiority of Nanocort compared to Depo-Medrol® in EULAR responders at Day 8 and to assess the safety of Nanocort in this study.

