1.1 Study Population

The study has been conducted at 21 sites in the Netherlands and Belgium. Sites were selected based on previous study experience in RA and accessibility to study required populations. The study population will consist of male and female subjects (≥ 18 years old) with active RA who are experiencing a flare / exacerbation defined as a recent increase in symptoms and a measured increase in DAS28 > 1.2 or > 0.6 if DAS28 ≥ 3.2 despite disease-modifying anti-rheumatic drugs (DMARDs) therapy or treatment naïve patients compared to last DAS28 measurement (maximum 6 months before screening).

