4.8 Efficacy Analysis

The primary and key secondary analyses will be completed for the ITT and PP populations.

Due to early termination of the study, the sample size will be much less than planned. As a result, the statistical power can be inadequate for the planned gatekeeping methodology. Therefore, standard hypothesis testing methods may be used instead to analyze the data.

[figure not shown]
To account for these possibilities and to facilitate better understanding of the data, the data will be analyzed 'as planned' in the protocol AND using more simple, unadjusted alpha analyses with basic chi-square tests. Therefore the data (Table 8A and 8B) will be analyzed two ways:

- Original Primary and Key Secondary Analyses using Hochberg's procedure and gatekeeping methods
- Modified Primary and Key Secondary Analyses using simple chi-square tests.

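### The planned site-adjusted logistic regression, read as one parameter per site, overstates the treatment log odds ratio by about 7-10% at planned size, and the SAP neither specifies nor withdraws it.

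*Combined protocol and SAP*

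**What the plan says.** Protocol 10.2 compares each Nanocort arm with Depo-Medrol on Day 8 EULAR response "using the Cochrane-Mantel-Haenszel test stratified by study site". As a sensitivity analysis, "a logistic regression model will be fitted on the EULAR responders with the stratification factor study site and additional baseline variables as covariates"; it adds that "Proportional odds ratios will be presented" and leaves the choice of extra covariates to the SAP. Protocol 10.3 analyses the three key secondary endpoints in the same way as the primary.

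On size, protocol 4.4 states: "A total of 330 subjects will be enrolled and randomized into 3 groups of 110 subjects", with the allowance "Taking a drop-out rate of approximately 10% into consideration". Protocol 4.1 states: "The study will be conducted at approximately 25 sites in the Netherlands, Belgium and the Czech Republic".

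The SAP describes a stopped trial. Section 1.1 says "The study has been conducted at 21 sites in the Netherlands and Belgium" and section 4.8 says "Due to early termination of the study, the sample size will be much less than planned". SAP 4.8 plans the Hochberg and gatekeeping analysis, described as following the protocol, and simple chi-square tests. It has no logistic model, covariate list or table for one. The opening of SAP section 4 undertakes to document every departure from the protocol. SAP 4.11 records three: two-sided hypotheses, removal of site stratification from the primary test, and the consequence of early termination. The logistic model is not mentioned.

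**The concern.** When a logistic model estimates a separate intercept for each of many small strata, ordinary maximum likelihood does not settle on the true treatment effect. The estimate is pushed away from zero and the test rejects too often. The problem depends on subjects per site, so a larger trial with proportionally more sites does not cure it, and a trial stopped early at 21 sites makes it worse.

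A sensitivity analysis is there to show whether the main result stands under another reasonable method. One that leans away from the null can seem to confirm an effect, or report a larger odds ratio than the data support. Because SAP 4.11 takes site out of the primary test, this model, if run, would be the only site-adjusted analysis of the primary endpoint described there.

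**Working it through.** **Inputs from the documents.** Planned 330 subjects in three equal arms. With 10% dropout, 110 × 0.9 = 99 per arm, or 297 in total and 198 per pairwise comparison. Sites: about 25 (protocol) or 21 (SAP). Allocation is 1:1:1, stratified by site.

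**Assumed inputs.** Response rates are redacted, and neither the achieved sample size nor the between-site variation is given. Setting A: control response 50%, true log OR 0.80, uneven sites. Setting B: 40% v 60%, so log OR = 2 × ln(1.5) = 0.811, mostly equal sites. Both use a site SD of 0.5 on the logit scale and blocks within site. Stopped size: 100 to 200 analysed.

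**No plan figure to reproduce.** The documents give no bias or test size for this model. The 110 per arm agrees with 99 evaluable plus 10% dropout; the rest of the sample size calculation is redacted.

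**Hand check.** With *m* subjects per site, the information used by ordinary maximum likelihood is about (*m* − 1)/*m* of the conditional (hypergeometric) information, while the score at the null is the same. The log OR is therefore inflated by about *m*/(*m* − 1), and the effective critical value is about 1.96 × √((*m* − 1)/*m*).

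- 297 at 25 sites: *m* = 11.9, inflation 1.092, critical value 1.876, size 6.1%.
- 198 (one pair) at 25 sites: *m* = 7.9, inflation 1.145, critical value 1.832, size 6.7%.
- 200 at 21 sites: *m* = 9.5, inflation 1.117, critical value 1.854, size 6.4%.
- 100 at 21 sites: *m* = 4.8, inflation 1.266, critical value 1.742, size 8.2%.

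This is an approximation near the null and omits ordinary small-sample bias, so simulation should come out somewhat higher for the odds ratio.

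**Simulation, setting B, one indicator per site.** Mean inflation of the log OR and size of the Wald test:

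| Analysed / sites | Inflation | Size at nominal 5% |
|---|---|---|
| 297 / 25, three-arm model | 10.0% | 5.9% (16,000 runs, SE 0.2 points) |
| 297 / 25, plus 3 covariates | 12.2% | 6.5% |
| 198 / 25, pairwise model | 15% | – |
| 200 / 21 | 14-15% | 6.0-6.2% |
| 165 / 21 | 18% | 6.8% |
| 120 / 21 | 28% | 6.4% |
| 100 / 21 | 34% | 7.7% |

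With all 330 analysed, inflation is 8.4%. Across planned-size three-arm settings the test size ran from 5.2% to 6.5%.

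**Simulation, setting A, ordinary v conditional logistic on the same data (700 runs).**

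- 330 / 25: 0.88 v 0.82, that is +10% v +2.5%; size 6.0% v 4.4%.
- 150 / 21: 0.91-0.94 v 0.80, that is +14-18% v 0%; size 7.3% v 4.4%.
- 100 / 21: 1.01-1.03 v 0.86, that is +26-29% v +7.5%; size 8.3% v 5.1%.

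A further run at a true log OR of 0.80 gave 0.86-0.87 at planned size (+7.5% to +9%), 0.96 at 150 and 1.03 at 100 with 21 sites.

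**On the odds ratio scale.** In setting B at planned size, a true 2.25 is reported as about exp(0.811 × 1.10) = 2.44. At 100 subjects it becomes exp(0.811 × 1.335) = 2.95.

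**Methods that condition on site.** In setting B the Mantel-Haenszel log OR is inflated by about 2% at 297, 2.5% at 200 and 5.5% at 120 (the last two at 21 sites). The site-stratified CMH test keeps its size (4.9% at 297 and 25 sites). So most of the inflation comes from the estimator.

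**The case against.** **The SAP governs the stopped trial and has no logistic model.** This is largely right. The protocol left the covariates to the SAP, which names none, so the model cannot be run as it stands. The stopped-trial figures therefore apply only if someone revives it. But the SAP undertakes to document departures and does not list this one, so the analysis has not been withdrawn either.

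**Ordinary maximum likelihood is not stated.** True. It is the natural reading when site is listed beside baseline variables as a covariate, but the text does not exclude a conditional, penalised or random-effect fit.

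**It is only a sensitivity analysis.** This stands and limits the severity. Study success does not depend on it.

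**The test is barely liberal at planned size.** This also stands. The 6.0% from 700 runs has a standard error of 0.9 points and cannot be told from 5%. The 5.9% from 16,000 runs can, but the excess is under one point. The bias in the odds ratio is the firmer finding.

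**Stronger readings to resist.** A reader might infer that the stopped trial's odds ratio is known to be 14-34% too high. The documents give no achieved sample size and the response rates are redacted, so that range is conditional on assumptions. A reader might also take the word 'Proportional' in "Proportional odds ratios will be presented" as a modelling error. With a yes/no outcome, a proportional-odds model is ordinary logistic regression, so the word is loose but changes no output.

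**Conclusion.** The point holds in limited form. If site enters as one parameter per site under ordinary maximum likelihood, the treatment log OR is overstated at planned size by about 7-10% in a three-arm model (about 12% with three extra covariates) and about 15% in pairwise models, with test size about 6-6.5%. With 100-200 subjects at 21 sites, the overstatement would be about 14-34% and the size about 6-9%.

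These figures rest on a control response of 40-50%, a site SD of 0.5 and a true log OR near 0.8, and the second set also on an assumed sample size. The hand check, which uses only subjects per site, agrees in direction and approximate size. Through protocol 10.3 the same issue reaches the key secondary endpoints.

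The gap between the documents needs no assumption: the protocol plans this analysis, and the SAP neither specifies it nor records its removal. It should be corrected, but it does not threaten the study's decision rule.

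**What to change.** State in SAP 4.8 whether the logistic sensitivity analysis is kept. If it is dropped, add that to SAP 4.11 with the reason.

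If it is kept:

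- Fit conditional logistic regression stratified by site (SAS PROC LOGISTIC with STRATA site) instead of site indicators.
- Name a short list of baseline covariates.
- Report the odds ratio of each Nanocort dose v Depo-Medrol with its 95% CI, and drop the word 'Proportional'.
- Record the change of method in SAP 4.11.

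The cost is one code statement and a few sentences. Sites where all or none respond drop out, but they carry no information on treatment in the ordinary model either. Some small-sample bias may remain at very small numbers: in setting A the conditional estimate was 0.86 against 0.80 with 100 subjects. A Mantel-Haenszel odds ratio, Firth penalisation or a random site effect would also be defensible; what matters is that one is named before unblinding.

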10.3 Key Secondary parameters

EULAR good responder at Day 8,

EULAR responder (good and moderate combined) at Day 15

EULAR good responder at Day 15.

The key secondary parameters will be analyzed as the primary study parameter EULAR responder at Day 8.

10.4 Secondary study parameters

10.4.1 EULAR Response

EULAR response (good, moderate, no response) at Week 1, 2, 3, 4, 6, 8, and 12

EULAR responses will be summarized by treatment group and the treatment groups will be compared by using the non-parametric Wilcoxon-Mann-Whitney test. .

10.4.2 DAS28 mean and % change

Absolute and % change from Baseline in DAS28 scores at 1, 2, 3, 4, 6, 8 and 12 Weeks will be submitted to an analysis of covariance, including baseline scores and study site as covariates or to an appropriate non-parametric alternative (e.g., Kruskal Wallis test). The time course of DAS28 scores will be submitted to a repeated measures analysis of variance.

10.4.3 Time to first EULAR response (moderate or good)

Time to first EULAR response, will be analyzed using the Kaplan-Meier method; comparison between treatment groups will be performed using the log-rank test.

10.4.4 ACR 20/50/70 response scores

The comparison of ACR20, ACR50 and ACR70 response rates among treatment groups will be analyzed using a stratified Cochrane-Mantel-Haenszel test, .

